3.3 Inclusion of Women and Minorities

Both men and women of all races and ethnic groups are eligible for this trial.

4. REGISTRATION PROCEDURES

4.1 General Guidelines for DF/HCC Institutions

Institutions will register eligible participants in the Clinical Trials Management System (CTMS) OnCore. Registrations must occur prior to the initiation of protocol therapy. Any participant not registered to the protocol before protocol therapy begins will be considered ineligible and registration will be denied.

An investigator will confirm eligibility criteria and a member of the study team will complete the protocol-specific eligibility checklist.

Following registration, participants may begin protocol therapy. Issues that would cause treatment delays should be discussed with the Overall Principal Investigator (PI). If a participant does not receive protocol therapy following registration, the participant's registration on the study must be canceled. Registration cancellations must be made in OnCore as soon as possible.

4.2 Registration Process for DF/HCC Institutions

DF/HCC Standard Operating Procedure for Human Subject Research Titled *Subject Protocol Registration* (SOP #: REGIST-101) must be followed.

4.3 General Guidelines for Other Investigative Sites

N/A

4.4 Registration Process for Other Investigative Sites

N/A

5. TREATMENT PLAN

5.1 Treatment Regimen by histology:

For melanoma: patients will be treated with the combination regimen of nivolumab 1 mg/kg combined with ipilimumab 3mg/kg Q3W (4 doses), followed by nivolumab monotherapy (480 mg Q4W) until progression or unacceptable toxicity.

For nonsmall cell lung cancer and head and neck cancer: patients will be treated with nivolumab 3mg/kg Q2W + ipilimumab 1mg/kg Q6W

For small cell lung cancer, breast cancer, and bladder cancer: patients will be treated with nivolumab 1mg/kg + ipilimumab 3mg/kg Q3W x 4 doses, followed by nivolumab 240 mg Q2W

For renal cell carcinoma and other solid tumors (not listed above): patients will be treated with nivolumab 3mg/kg + ipilimumab 1mg/kg Q3W x 4 doses, followed by nivolumab 480 mg Q4W

Each treatment cycle will be 6 weeks, with the exception of the nivolumab maintenance monotherapy phase in melanoma, renal cell carcinoma and other solid tumors, when each cycle will be 8 weeks. Treatment will be administered on an outpatient basis. Reported adverse events and potential risks are described in Section 7. Appropriate dose modifications are described in Section 6. No investigational or commercial agents or therapies other than those described below may be administered with the intent to treat the participant's malignancy.

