5.3 Agent Administration

For treatment schedule, see section 5.1

When study drugs (ipilimumab or nivolumab) are to be administered on the same day, separate infusion bags and filters must be used for each infusion. It is recommended that nivolumab be administered first. The second infusion will always be ipilimumab, and will start approximately 30 minutes after completion of the nivolumab infusion. The ipilimumab infusion will start no

SOONER than 30 minutes after completion of nivolumab infusion. An infusion window of +/- 10 minutes is allowed for both study drugs Nivolumab & Ipilimumab.

BMS-936558 (nivolumab) is to be administered as a 30 minute IV infusion. Ipilimumab should be administered as a 30 minute infusion following.

Ipilimumab and nivolumab may be diluted in 0.9% Sodium Chloride Solution or 5% Dextrose solution.

The dosing calculations should be based on the body weight. If the subject's weight on the day of dosing differs by > 5% from the weight used to calculate the dose, the dose must be recalculated. All doses should be rounded up or to the nearest milligram per institutional standard.

For the q3 week schedule, patients may be dosed no less than 18 days from the previous dose of drug; and dosed up to 3 days after the scheduled date if necessary.

For the q4 week schedule, patients may be dosed no less than 24 days from the previous dose of drug; and dosed up to 3 days after the scheduled date if necessary.

There will be no dose modifications permitted. Dose reductions or dose escalations are not permitted.

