10. STUDY CALENDAR

Baseline evaluations are to be conducted within 14 days prior to start of protocol therapy, with the exception of CSF with positive cytology, which must be done \leq 6 weeks prior to initiation of study treatment. Also, if patients received other chemotherapy or targeted therapy within 14 days prior to start of protocol therapy, CBC and serum chemistry (including LFTs and creatinine) should be done within 5 days prior to start of protocol therapy. Scans and x-rays must be done \leq 4 weeks prior to the start of therapy. In the event that the participant's condition is deteriorating, laboratory evaluations should be repeated within 48 hours prior to initiation of the next cycle of therapy.

Assessments must be performed prior to administration of any study agent. Study assessments and agents should be administered within \pm 3 days of the protocol-specified date, unless otherwise noted.

Calendar During Induction Phase for Melanoma, Small Cell Lung Cancer, Breast Cancer, Bladder Cancer, Renal Cancer and Other Solid Tumors

	Pre-Study	Wk 1	Wk 2	Wk 3	Wk 4	Wk 5	Wk 6	Wk 7	Wk 8	Wk 9	Wk 10	Wk 11	Wk 12	Off Study ^h	Follow-up visits ⁱ
Ipilimumab		A			A			A			A				
Nivolumab		B			B			B			B				
Informed consent ^a	X														
Demographics ^a	X														
Medical history ^a	X														
Concurrent meds	X	X-----X													
Physical exam ^b	X	X	X	X	X	X	X	X	X	X	X	X	X	X	X
Vital signs	X	X	X	X	X	X	X	X	X	X	X	X	X	X	X
Height	X														
Weight	X	X			X			X			X			X	X
Performance status	X	X			X			X			X			X	X
CBC w/diff, plts	X	X			X			X			X			X	X
Serum chemistry ^c	X	X			X			X			X			X	X
EKG (as indicated) ^d	X														
Adverse event evaluation		X-----X												X	X
Tumor measurements	X	Tumor measurements are repeated every 6 weeks. Documentation (radiologic) must be provided for participants removed from study for progressive disease.												X	
Radiologic evaluation	X	Radiologic measurements should be performed every 6 weeks (Brain MRI and CT Chest/Abd/Pelvis)												X	X
B-HCG	X ^e							X							X
Cerebrospinal fluid	X ^f	X			X			X			X				
Blood ⁱ	X	X			X			X			X			X	X
Archival tissue ^g	X													X	X

A: For melanoma, small cell lung cancer, breast cancer, bladder cancer and other solid tumors (except NSCLC and head and neck cancers): Ipilimumab 3mg/kg every 3 weeks x 4 doses during induction.. For renal cell cancer: Ipilimumab 1mg/kg every 3 weeks x 4 doses during induction.

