B: For melanoma, small cell lung cancer, breast cancer, bladder cancer and other solid tumors (except NSCLC and head and neck cancers): Nivolumab 1mg/kg every 3 weeks for 4 doses during induction. For renal cell cancer: nivolumab 3mg/kg every 3 weeks x 4 doses during induction.

^aAll screening procedures to be performed within 14 days of start of study treatment, with the exception of CSF with positive cytology, which can be 6 weeks prior to initiation of study treatment. C1D1 and Day 1 of subsequent cycles: For C1D1 only, screening assessments may serve as day 1 assessments, except serum pregnancy (within 72 hours of drug) and except in the event that there are any indications that the participant's condition is deteriorating for which laboratory evaluations should be repeated within 48 hours prior to initiation. For all subsequent cycles, required assessments should be performed within 3 days of scheduled cycle day 1.

^bPhysical examination must include neurologic assessment.

^cSerum chemistries: Serum chemistry tests include albumin, amylase, lipase, BUN, creatinine, ALT, AST, LDH, serum alkaline phosphatase, direct and total bilirubin, glucose, total protein, sodium, potassium, chloride, HCO3, calcium, uric acid and TSH. A reflexive free T4 and free T3 will be performed reflexively for out of range TSH values. Patients should also be tested for Hepatitis B virus surface antigens (HBV sAg) and hepatitis C virus ribonucleic acid (HCV antibodies) at screening only.

^dEKG should be obtained at baseline for screening and then as clinically indicated

^eSerum pregnancy test (women of childbearing potential) is required within 72 hours of C1D1 dose. Pregnancy will be performed every 6 weeks while on treatment, and at 30 days and 70 days post last dose of Nivolumab

^fCerebrospinal fluid will be collected every 3 weeks during the induction phase and every 4 weeks during the maintenance phase to assess disease status (will be sent for cell count, protein, glucose, cytology) and 10cc will be saved for correlative studies as described in Section 9.0

^gTissue collected as part of clinical care (e.g. from prior biopsy, craniotomy) will be collected. See Section 9 for specimen collection

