B: For melanoma, renal cell carcinoma and other solid tumors: Nivolumab 480 mg Q4 weeks during maintenance phase

C: For small cell lung cancer, breast cancer and bladder cancer: nivolumab 240mg every 2 weeks during maintenance phase

^aAll screening procedures to be performed within 14 days of start of study treatment, with the exception of CSF with positive cytology, which can be 6 weeks prior to initiation of study treatment. C1D1 and Day 1 of subsequent cycles: For C1D1 only, screening assessments may serve as day 1 assessments, except serum pregnancy (within 72 hours of drug) and except in the event that there are any indications that the participant's condition is deteriorating for which laboratory evaluations should be repeated within 48 hours prior to initiation. For all subsequent cycles, required assessments should be performed within 3 days of scheduled cycle day 1.

^bPhysical examination must include neurologic assessment.

^cSerum chemistries: Serum chemistry tests include albumin, amylase, lipase, BUN, creatinine, ALT, AST, LDH, serum alkaline phosphatase, direct and total bilirubin, glucose, total protein, sodium, potassium, chloride, HCO₃, calcium, uric acid and TSH. A reflexive free T4 and free T3 will be performed reflexively for out of range TSH values. Patients should also be tested for Hepatitis B virus surface antigens (HBV sAg) and hepatitis C virus

ribonucleic acid (HCV antibodies) at screening only.

^aEKG should be obtained at baseline for screening and then as clinically indicated

^bSerum pregnancy test (women of childbearing potential) is required within 72 hours of C1D1 dose. Pregnancy will be performed every 6 weeks while on treatment, and at 30 days and 70 days post last dose of Nivolumab.

^cCerebrospinal fluid will be collected every 4 weeks during the maintenance phase to assess disease status (will be sent for cell count, protein, glucose, cytology) and 10 cc will be saved for correlative studies as described in Section 9.0

^dTissue collected as part of clinical care (e.g. from prior biopsy, craniotomy) will be collected. See Section 9 for specimen collection requirements

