Dose selection for Nivolumab should be assigned per subject as outlined in the study drug dosing section of the clinical protocol. When Nivolumab is administered in combination with Ipilimumab, the Nivolumab will be infused first, followed by the ipilimumab to start approximately 30 minutes after the Nivolumab infusion completion.

Preparation examples are listed below assuming at 77.2 kg patient weight.

Example 1: 1 mg/kg dose (rounding to nearest mg dose)

Nivolumab 77 mg (7.7 ml Nivolumab 10mg/ml solution, local rounding rules applicable) may be mixed with 52.3 ml NS or D5W to a total volume = 60 ml (concentration = 1.3 mg/ml) which can be infused over 30 minutes (+/- 6 min) at 1ml/min followed by flush

Example 2: 3 mg/kg dose (rounding to the nearest mg dose)

Nivolumab 232 mg (23.2 ml Nivolumab 10mg/ml solution, local rounding rules applicable) may be mixed with 36.8 ml NS or D5W to a total volume = 60 ml (concentration = 3.9 mg/ml) which can be infused over 30 minutes (+/- 6 min) at 1 ml/min followed by flush.

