****** Remember to check the [ALERT PAGE](#)******

SPECIAL NURSING CONSIDERATIONS UNIQUE TO THIS PROTOCOL

Study Design	
 Ipilimumab is a fully human monoclonal immunoglobulin (Ig) specific for human cytotoxic T lymphocyte antigen 4, which is expressed on a subset of activated T cells (Section 2.2.1) Nivolumab is a fully human monoclonal antibody that targets the PD-1 CD279 cell surface membrane receptor (Section 2.2.2) A cycle is defined as six weeks, with the exception of the nivolumab maintenance monotherapy phase in melanoma and renal cell carcinoma a cycle when each cycle will be 8 weeks (Section 5.1)
Dose Calc.	
 Nivolumab will be dosed as mg /kg Ipilimumab will be dosed as mg /kg The dosing calculations should be based on the body weight. If the subject's weight on the day of dosing differs by > 5% from the weight used to calculate the dose, the dose must be recalculated (Section 5.3)
Study Drug Administration	
Agent Administration Guidelines are found in Section 5.3
 
 For treatment schedule by histology, see Section 5.1. When study drugs are to be administered on the same day, separate infusion bags and filters must be used for each infusion. Nivolumab will be administered first. Ipilimumab will be administered approximately 30 minutes after completion of Nivolumab. The Ipilimumab infusion will start no sooner than 30 minutes after completion of Nivolumab infusion. An infusion window of +/- 10 minutes is allowed for both Nivolumab and Ipilimumab The criteria to treat is outlined in Table 1, and in section 5.2. Nivolumab is to be administered as a 30 minute IV infusion. Ipilimumab is to be administered as a 30 minute IV infusion.
Dose Mods & Toxicity	
Criteria to Treat, Dose Modifications/Dosing Delays for Toxicity are outlined in Sections 5.2 and 6
 
 There will be no dose modifications permitted. Dose reductions or dose escalations are not permitted (Section 5.3 and 6) This protocol uses NCI CTCAE criteria, version 4.0
Con Meds	
Concomitant Therapy Guidelines are in Section 5.4
 
 Antiemetic premedications should not be routinely administered prior to dosing of drugs. See Section 6 for premedication recommendations following a nivolumab or ipilimumab related infusion reaction

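### For solid tumors outside the named list, Section 5.1 and the induction calendar give reversed nivolumab and ipilimumab doses, and nothing says which governs

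*Combined protocol and SAP*

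**What the plan says.** Section 5.1 sets the regimen by histology. It groups unlisted solid tumors with renal cell carcinoma: "For renal cell carcinoma and other solid tumors (not listed above): patients will be treated with nivolumab 3mg/kg + ipilimumab 1mg/kg Q3W", for four doses, followed by flat-dose nivolumab.

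The induction calendar in Section 10 groups unlisted solid tumors instead with melanoma, small cell lung, breast and bladder cancer. Footnote A gives "other solid tumors (except NSCLC and head and neck cancers): Ipilimumab 3mg/kg every 3 weeks x 4 doses during induction". Footnote B gives "other solid tumors (except NSCLC and head and neck cancers): Nivolumab 1mg/kg every 3 weeks for 4 doses during induction". The other pair is kept for one histology: footnote B continues "For renal cell cancer: nivolumab 3mg/kg every 3 weeks x 4 doses during induction", and footnote A gives renal cell cancer ipilimumab 1 mg/kg.

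Maintenance dosing is not in dispute. Section 5.1 and the maintenance calendar's footnote B agree: "For melanoma, renal cell carcinoma and other solid tumors: Nivolumab 480 mg Q4 weeks during maintenance phase".

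Three places direct staff to a dosing source. Section 5.3 says "For treatment schedule, see section 5.1". The nursing education sheet says "For treatment schedule by histology, see Section 5.1". The pharmacy manual, Section 3.1.2, says "Dose selection for Nivolumab should be assigned per subject as outlined in the study drug dosing section of the clinical protocol", without naming a section number.

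**The concern.** Two current parts of the protocol give explicit mg/kg instructions for the same patients, and the instructions are reversed. Whichever one staff follow, they depart from the other. Section 3.1.1 admits any solid tumor, so patients in this group can be enrolled.

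The stake is patient dosing. If Section 5.1 is right, a patient dosed from the calendar receives too much ipilimumab and too little nivolumab. If the footnotes are right, a patient dosed from Section 5.1 receives the opposite. Sections 5.3 and 6 prohibit dose reductions, so the protocol offers no later step-down for a patient started on the higher ipilimumab dose.

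**Working it through.** **Step 1: set the two sources side by side (induction, every 3 weeks, four doses).**

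| Histology | Section 5.1 (nivolumab / ipilimumab, mg/kg) | Calendar footnotes A and B (nivolumab / ipilimumab, mg/kg) | Agree? |
|---|---|---|---|
| Melanoma | 1 / 3 | 1 / 3 | Yes |
| Small cell lung, breast, bladder | 1 / 3 | 1 / 3 | Yes |
| Renal cell | 3 / 1 | 3 / 1 | Yes |
| Other solid tumors | 3 / 1 | 1 / 3 | **No, reversed** |

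Non-small cell lung and head and neck cancer have their own calendar, which matches Section 5.1 (nivolumab 3 mg/kg every 2 weeks, ipilimumab 1 mg/kg every 6 weeks). The conflict is therefore confined to primaries other than melanoma, non-small cell lung, head and neck, small cell lung, breast, bladder and renal.

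**Step 2: rule out a misreading.** Both footnotes place the group with the 1/3 pair, each names the group in words, and the calendar's title includes it. A single mistyped digit or a broken table would not produce this. The text is current, not an amendment log.

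**Step 3: size of the difference, calendar against Section 5.1.**

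- Ipilimumab per dose: 3 / 1 = 3 times. Over four doses: 4 × 3 = 12 against 4 × 1 = 4 mg/kg.
- Nivolumab per dose: 1 / 3 = one third. Over four doses: 4 × 1 = 4 against 4 × 3 = 12 mg/kg.

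**Step 4: in milligrams, at the pharmacy manual's example weights** (77 kg in its ipilimumab section, 77.2 kg in its nivolumab section, rounded to the nearest mg as there).

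- Ipilimumab, 77 kg: 3 × 77 = 231 mg against 1 × 77 = 77 mg per dose. Over four doses: 4 × 231 = 924 against 4 × 77 = 308 mg.
- Nivolumab, 77.2 kg: 1 × 77.2 ≈ 77 mg against 3 × 77.2 = 231.6 ≈ 232 mg per dose. Over four doses: 4 × 77 = 308 against 4 × 232 = 928 mg.

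The four-dose totals are maxima; delays or discontinuation would lower them.

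**Step 5: does any text settle the conflict?** Section 5.3 and the nursing sheet point to Section 5.1, but neither says that it overrides the calendar. The pharmacy manual sends both drugs back to a study-drug section of the protocol that it does not identify by number. Its dose worksheet cites a protocol appendix section 4, yet the appendices are lettered A and B, and Section 4 of the protocol covers registration. The manual's only worked ipilimumab example uses 3 mg/kg, so an order written from the calendar would not look unusual to a pharmacist.

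**The case against.** The best case on the other side is that the gap is narrow in practice and the consequences are limited.

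- **The pointers run one way.** Section 5.1 is the regimen section, Section 5.3 and the nursing sheet both send staff there, and no text sends them to the calendar for mg/kg doses. The pharmacy manual also redirects ipilimumab dosing, in its Section 3.2.2, to the protocol's dosing section. This makes the footnotes the probable error. It is still not a precedence rule, and the footnotes are explicit dosing text.
- **Neither pair is an untested overdose.** In the phase 1 study described in Section 2.2.3, nivolumab 1 with ipilimumab 3 mg/kg was the maximum tolerated dose, and only 3 with 3 exceeded it. Section 5.1 uses the 1/3 pair for four other histologies. The documents show no overall toxicity difference between the two pairs. This stands, with the caveat that the phase 1 data are in melanoma.
- **Few patients are likely to be affected.** Sections 2.1 and 2.3 say that leptomeningeal disease arises most often from lung cancer, breast cancer and melanoma, whose doses are consistent, and accrual is at most 20. This is a fair inference, but no count is given.
- **The primary analysis is untouched.** The 3-month survival rate already pools several regimens, and the dose given should be recoverable from the Treatment Forms (Section 12.1.2). Both points stand. The forms, however, record a dosing error only after it has happened.

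These arguments limit the harm. They do not reconcile the two instructions.

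**Conclusion.** The inconsistency is real and should be corrected. For unlisted solid tumors the two sources differ by a factor of three for each drug, in opposite directions. The dose ratios come directly from the text; only the milligram figures depend on the example weights.

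The footnotes are probably wrong and Section 5.1 right, but that is an inference from cross-references, and only the sponsor can confirm it. If the footnotes were intended, Section 5.1 must change instead.

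The point concerns dosing safety and protocol consistency. It does not alter the 3-month survival endpoint, the two-stage decision rule or the error rates. The number of patients exposed to the conflict is unknown and may be zero.

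**What to change.** 1. The sponsor confirms the intended induction dose for unlisted solid tumors.
2. If Section 5.1 governs, amend induction calendar footnotes A and B to move this group to nivolumab 3 / ipilimumab 1 mg/kg, or replace the footnote doses with a reference to Section 5.1. While doing so, add the group to the row label for every-4-week nivolumab in the maintenance calendar, which names only melanoma and renal cell carcinoma although its footnote covers all three.
3. State that Section 5.1 takes precedence for dosing.
4. Notify prescribing, pharmacy and nursing staff before any further patient in this group is treated. The documents do not show whether enrollment is still open; if it has closed and no such patient is on treatment, this step falls away.
5. Check the Treatment Forms of any patient already treated in this group, and report safety and 3-month survival descriptively by regimen received. With so few patients the survival breakdown would serve transparency rather than inference. The endpoint definition and decision rule stay as they are.

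The cost is an amendment to two footnotes and a row label, one sentence on precedence, a staff notice and a short record check. It needs no extra patients and no design change.

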5.2 Pre-Treatment Criteria

5.2.1 Cycle 1, Day 1

A serum or urine pregnancy testing is required within 72 hrs of study enrollment. Cycle 1, Day 1 labs will be used to confirm eligibility.

System	Laboratory Value
Hematological	
Absolute neutrophil count (ANC)	$\geq 1500 / \text{mcL}$
Platelets	$\geq 100,000 / \text{mcL}$
Hemoglobin	$\geq 9 \text{ g/dL}$ or $\geq 5.6 \text{ mmol/L}$ without transfusion or EPO dependency (within 7 days of assessment)
Renal	
Serum creatinine OR Measured or calculated ^a creatinine clearance (GFR can also be used in place of creatinine or CrCl)	$\leq \text{ Serum creatinine} \leq 1.5 \times \text{ULN}$ or creatinine clearance (CrCl) $\geq 40 \text{ mL/min}$ (if using the Cockcroft-Gault formula below): $\text{Female CrCl} = \frac{(140 - \text{age in years}) \times \text{weight in kg} \times 0.85}{72 \times \text{serum creatinine in mg/dL}}$ $\text{Male CrCl} = \frac{(140 - \text{age in years}) \times \text{weight in kg} \times 1.00}{72 \times \text{serum creatinine in mg/dL}}$
Hepatic	
Serum total bilirubin	$\leq 1.5 \times \text{ULN}$ OR
	Direct bilirubin $\leq \text{ULN}$ for subjects with total bilirubin levels $> 1.5 \text{ ULN}$
AST (SGOT) and ALT (SGPT)	$\leq 3 \text{ ULN}$ OR $\leq 5 \times \text{ULN}$ for subjects with liver metastases
Albumin	$\geq 2.5 \text{ mg/dL}$
Coagulation	
International Normalized Ratio	$\leq 1.5 \times \text{ULN}$ unless subject is receiving anticoagulant therapy

(INR) or Prothrombin Time (PT)	as long as PT or PTT is within therapeutic range of intended use of anticoagulants $\leq 1.5 \times \text{ULN}$ unless subject is receiving anticoagulant therapy
Activated Partial Thromboplastin Time (aPTT)	as long as PT or PTT is within therapeutic range of intended use of anticoagulants
^a Creatinine clearance should be calculated per institutional standard.	

